1.0 Research Synopsis

Study Title: Marijuana in combination with opioids for pain and symptom control in hospice patients.

Clinical Phase: Exploratory/Pilot (Phase I)

IND Sponsor N/A

2.0 Background and Significance

The Connecticut Hospice, Inc., the first Hospice who served for four decades in the United States, recently received The Joint Commission 's first advanced palliative hospital certification without recommendations for improvement, embarks on a new study.

Hospice care (Johnson-Hurzeler 1998) involves managing symptoms and quality of life for patients whose life expectancy is less than six months. (Kruse 2013) A study involving 100 hospice inpatients revealed high incidence of many symptoms, including chronic pain (62% of patients), anorexia (58%), constipation (52%), nausea (37%), vomiting (24%), sleep issues (22%), and anxiety (19%). (Potter 2003) The majority of hospice patients are prescribed opioids for pain control. The typical process involves administering a certain dosage of opioids and, depending upon pain relief and side effects, the dosage (in mgs) may be adjusted accordingly in increments of 25%. Common side effects of opioid medications include constipation, nausea, sedation, respiratory depression, dependence, and death. (Bruehl 2014)

In studies to date, marijuana has shown promise as an adjunctive medication for patients who require opioids for pain management. (Karst 2009) An Australian study—POINT (Pain and Opioids in Treatment)—collected reports from 1,514 patients on the efficacy of marijuana in combination with opioids for management of pain from a diverse range of causes. (Degenhardt 2015) In general, patients reported that the combination of marijuana and opioids was more effective for pain relief than opioids alone. (Degenhardt 2015) Another study, which included 21 patients suffering from chronic pain, found increased efficacy in pain control with the addition of marijuana to opioid regimens; investigators concluded that addition of marijuana to opioid regimens may result in a lowered effective dose of opioids. (Abrams 2011) In the same study, investigators reasoned that marijuana facilitates the activities of opioids either by slowing opioid

metabolism or by increasing plasma opioid levels. (Abrams 2011) Marijuana may also facilitate the pain-relieving effects of opioid medications by acting upon opioid receptors. (Cichewicz 2004; Abrams 2011) Animal studies have shown the possibility of direct interaction between cannabinoid and opioid receptors. (Bushlin 2010) In studies, marijuana has been shown to reduce pain associated with multiple sclerosis, HIV, chronic neuropathic pain, rheumatoid arthritis, and acute pancreatitis. (Fine 2013) Surveys of medical marijuana have shown that the drug can improve pain and control insomnia with minimal side effects in some patients. (Wilsey 2008) Marijuana is also known to help mitigate nausea and vomiting. (Sharkey 2014) Dronabinol, a pill which is chemically identical to THC, was approved in 1992 by the FDA as an appetite stimulant in AIDS patients. (Grant 2005) The latter may indicate the use of marijuana for hospice patients experiencing anorexia.

Most studies of the medical benefits of marijuana so far have included fewer than 200 patients. Federal restrictions make it difficult for the research to advance. Marijuana is currently characterized by the Federal Government as a Schedule-I controlled substance, meaning that according to federal law, "(A) The drug or other substance has a high potential for abuse. (B) The drug or other substance has no currently accepted medical use in treatment in the United States. (C) There is a lack of accepted safety for use of the drug or other substance under medical supervision." (21 U.S. Code *812) The DEA and FDA have yet to grant their approval for largescale studies of the medical applications of marijuana; however, in 2014, the FDA vowed to reexamine the scheduling of marijuana so that more large-scale research could perhaps be conducted. (Ferner 2014)

In 2012, Connecticut lawmakers passed a law allowing for the palliative use of marijuana. The law enables doctors to prescribe marijuana (i.e. dried leaves) and its derivatives (i.e. oils, waxes, edibles, transdermal, and sublingual preparations) to patients suffering from specific conditions.

Under Connecticut state law "Debilitating Medical Condition" includes Cancer or terminal illness requiring end-of-life care. This study specifically will enroll cancer and non-cancer patients as a primary diagnosis suffering from pain and having a terminal illness (defined as having less than 6 months to live) requiring end of life care. Table-I .(pg. 8) Originally published in Cancer Therapeutics in 1998, and revised in 2016, includes the specific inclusion diagnoses for this study). Under the international classification of disease (ICD-10), these diagnoses are categorized in The Connecticut Hospice-Hospital database for fiscal year 2016, representing patients that have been referred and admitted.

Table 1.

The Connecticut Hospice, Inc.

SUMMARY GUIDELINES FOR INITIATION OF ADVANCED CARE

(OVER FOR REFERRAL INFORMATION)

Authored by: [name].

[name], MPH, HA

Limited response to additional therapy expected and not durable.

First-line salvage therapies have failed. Less than 30% response to second-line or other therapy expected and not durable.

Dementia beyond Stage 7 of the Functional Assessment Staging Scale for Alzheimer's Disease or multi-symptoms present and declining functional status (Karnofsky and when there is partial or total dependence in ADLs.)

Progressive nerve degeneration with resultant partial/total paresis or paralysis of extremities and muscles of respiration. Optimal therapy reached. (i.e. no further response to therapies expected). With major symptoms present and declining functional status (Karnofsky 50% and when there is partial or total dependence in ADLs).

Massive CVA with no rehabilitation potential; patient unable to eat. Optimal therapy reached (i.e. no further response to therapies expected, with major symptoms present and declining functional status (Karnofsky and when there is partial or total dependence in ADLs).

Congenital defects, complication of infections, or trauma based upon individual case review.

Long-standing history of congestive heart failure or multiple MI. Class IV NY Heart Association Symptoms and ejection fraction. No further responses expected to medical therapy and no options for CABG, grafting, angioplasty, pacemaker, or transplant. Any one of the following: dyspnea, angina, orthopnea, edema. Any two of the following: Karnofsky <50%, minimal activity tolerance, dependence on 20 or more ADLs.

Degradation of PFTs: FEV1 after bronchodilator <30 % of predicted, decrease in FEV1 on yearly serial testing of >40ml/year. Cor pulmonale, Hypoxemia, significant CO₂ retention as measured by ABGs. Optimal therapy reached with multiple bronchodilators and steroid dependence with dyspnea (of any kind) and O₂ dependence. Declining functional status including Karnofsky <50%, chair-bound, minimal activity tolerance, and dependence on 2 or more ADLs.

Worsening LFTs and documented evidence of disease (utilizing abdominal ultrasound, CT, HIDA Scan, Cholangiography, ERCP or any appropriate diagnostic imaging demonstrating biliary obstruction, hepatic vein occlusion, hepatic artery thrombosis, hepatocellular dysfunction. No expectation of success from medical management and/or surgical intervention. Presence of any one major symptom and declining function status (Karnofsky <50% and dependence in 2 or more ADLs).

10. Decision made to stop dialysis with one of the following conditions: chronic dialysis necessary to sustain life, disease progression despite interventions, intolerable associated medical complications of non-renal disease. In addition, at least one of the following: peripheral vascular disease degradation, hypotension, dementia, depression, resistance to dialysis Rx; and, declining functional status.

11. CD4<50 with concurrent ongoing major infections, and the presence of at least one of the following: lymphoma, Kaposi's Sarcoma, PMH, HIV encephalopathy, HIV wasting syndrome. Progression of disease on antiretroviral therapy and the presence of major symptoms with declining function status.

Important Note on these Guidelines: The footnotes above are an integral part of these guidelines. They must be used in conjunction with the matrix at the left. Cancer Therapeutics: May/June 1998*Vol 1, No.2

Disease Category	Initial Diagnosis	Refer to Advanced Care upon		
		Recurrence	Progression	Critical Clinical Decision
Cancer				
Brain/CNS Tumor				
Breast				
Colorectal				
Esophagus				
Gall Bladder				
Head & Neck				
Leukemia				
Liver				
Lung				
Lung - inoperable				
Melanoma				
Ovarian - inoperable				
Ovarian/GYN				
Pancreatic				
Prostate/GU				
Renal				
Sarcoma				
Stomach Non-Hodgkin's Lymphoma				
End-Stage Diseases				
Neurological: Alzheimers Disease				
ALS		4		
CVA			5	
MS			4	
Congenital, Infectious, or Traumatic Disability				
Heart Failure		7		
Lung-COPD		8		
Liver Failure/ Cirrhosis		9		
Kidney Failure			10	
AIDS		11		

Options:
In
R

P
C
D

F
1.
2.

3.

4.

5.

6.

7.

8.

9.

10.

Initial Diagnosis: The first diagnosis of disease by a physician.

Recurrence: Subsequent diagnosis of same disease resulting from limited response to additional therapy expected and not durable.

Progression: Continuation of disease process.

Critical Clinical

Decision: Consensus decision made by physician, patient, and family that want to forego any continuing curative or rehabilitative treatment.

Footnotes

All patients participating in this study will be registered as medical marijuana patients in accordance with state law. This study will provide a basis for expanding the indications for which marijuana can legally be prescribed in the state of Connecticut, thereby benefiting additional patients.

The constituents of marijuana that have been most extensively studied for therapeutic purposes so far are A9-tetrahydrocannabinol (A9-THC) and cannabidiol (CBD). (Fine 2013) A9-THC acts primarily on Cannabinoid-1 receptors (CB1), which are most densely concentrated in central nervous tissue (brain and spinal tissue); CBD acts primarily on Cannabinoid-2 receptors (CB2), which exist mostly in peripheral tissues (all other tissues). (Fine 2013) Activation and inhibition of cannabinoid receptors affects pain perception, cognition and memory, locomotor activity, endocrine functions, temperature control and heart rate, nausea and vomiting, intraocular pressure, inflammation, and immune recognition and antitumor activity. (Fine 2013) Both CB-1 and CB-2 receptors are involved in regulating inflammatory pain. (Elikottil 2009) Relevantly for this study, A9-THC and CBD's actions upon cannabinoid receptors may reduce inflammation and pain. (Fine 2013) Furthermore, A9-THC has been shown to reduce nausea and vomiting. (Fine 2013) Whereas higher doses of A9-THC have been associated with adverse psychological effects—e.g. psychosis-like symptoms and motor and cognitive impairment—CBD seems to block, to a certain extent, those adverse psychological and cognitive effects of A9-THC. (Solowij 2014) Evidence of a physiological basis for the opposing effects of A9-THC and CBD emerged through an fMRI study in which researchers cross-referenced the behavioral effects of these substances with their respective fMRI images. (Bhattacharyya 2010)

The research summarized above demonstrates the potential role of marijuana and its derivatives in the treatment of chronic pain—whether inflammatory or neuropathic—nausea, vomiting, sleep disorders, and wasting syndrome. Identification of a combination therapy that is safer and/or more effective than current approaches is a desirable prospect. Clinical trials utilizing Sativex an oral mucosal spray containing THC and CBD, approved in Canada for the spasticity associated with MS, and Marinol a synthetic oral THC product FDA approved in the United States provide evidence for efficacy and safety of oral THC containing treatments. The protocol is justified by the potential benefits of marijuana, the risks of opioid monotherapy, and the lack of research regarding opioid-marijuana combination therapy for improved pain control in hospice patients.

The primary goal of this study is to further substantiate marijuana's role in pain management, specifically for the hospice patient. The drug preparations used in the study will be administered orally. The dosage will be marijuana containing a 30:1 CBD:THC ratio. Either 40 mg/l .5 mg or 80 mg/3 mg. Safety and efficacy data on THC and CBD can be cited in various clinical studies. The product to be utilized is based on current clinical published research (Partial references 21 , 26, 37) utilizing CBD and THC as the main cannabinoids. The study drug will be provided by NIDA (The National Institute for Drug Safety).

3.0 Objectives

Primary

1. Improve pain management as identified by decreased overall numeric pain scores
2. Reduce opioid dosage increases
3. Reduce overall opioid utilization

Secondary

Evaluate changes in patient weight, appetite, nausea and vomiting, O2 saturation, feelings of well-being, anxiety, and depression.

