4.0 Study Design and Methodology

Design

This will be an open-label study. Patients will choose to participate in a Marijuana adjuvant treatment group, receiving marijuana in combination with standard opioid therapy.

The goal is to enroll at least 66 Hospice patients in the study.
Methodology

Patients will be notified of the study's existence through communication with the study's investigation team at time of admission. Patients will be screened for study eligibility—see section 6.0 for study eligibility factors—and if the patient is both eligible and interested in participating, the sub-investigator will discuss and review the informed consent form with the patient and obtain their signature; the patient will then have a consultation with a prescribing physician; and, if the physician has determined that medical marijuana is a viable option for that patient, registration with the Connecticut Medical Marijuana program will begin. For patients who have already been prescribed both marijuana and opioid medication upon admission to Hospice, signing the consent form will complete study enrollment.

Patients' initial opioid dose, dosing schedule and numeric pain score will be recorded. For the duration of the study (at least five days) changes in opioid doses and numeric pain scores will be tracked daily.

Marijuana will be administered to the patient via oral route three times daily for at least five days. Patients will receive CBD:THC product provided by NIDA.

On admission to the study, a modified Edmonton Symptom assessment scale to quantify baseline appetite, depression, nausea, vomiting, overall well-being, and anxiety.

Data Tracking: Primary objective tracking will include average numeric pain scores and number of opioid dosage increases and average daily opioid amount (mg equivalents of morphine).

Secondary objectives include Weight, Appetite, N/V, O2 Saturation, Self-reported data points from the modified Edmonton Assessment Scale.

Data Tracking Intervals: Primary objective tracking of pain will be daily every 4 hours (twice per shift). Secondary objective tracking as follows: Weight daily, Appetite every 8 hours (every shift), N/V, O2 saturation as reported by clinician documentation, Edmonton scale results three times weekly.

Analysis

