Following the data collection phase, investigators will calculate average numeric pain scores, average number of increases in opioid dosage and average daily opioid amount (mg equivalents of morphine). Analysis will examine whether the addition of CBD/THC with opioid therapy had

a stabilizing effect or improvement in pain management (lower average numeric pain scores, few dosage increases, lower opioid doses and subsequently less opioid therapy needed)

Additionally calculations will include results of changes in weight, calculation of average changes in O2 saturation, and average changes in Edmonton-Scale scores for secondary data collection points.

Patient Selection to Ensure Validity

The study will enroll patients with a primary diagnosis (Table 1) of cancer and non-cancer with associated pain considered to have a terminal illness requiring end of life care, utilizing routine or as needed opioid therapy for pain.

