5.0 Study Population

Adult (≥18 years of age), non-pregnant, alert and oriented hospice inpatients. Subjects must take opioids for pain management either routinely scheduled or on an as needed basis to qualify.

Inclusion / Exclusion Criteria

Included: alert adults (age 18+) requiring opioids for pain management (routine or as needed) with a cancer diagnosis or non-cancer diagnosis as their terminal illness as defined in Table 1 .

Excluded: pregnant women, children (patients < 18 years of age), minimally or unresponsive patients unable to take oral medications, and agitated combative patients.

Sample Size

66 patients is the target.

The average length of stay at The Connecticut Hospice, Inc. is twelve days. At the end of each nine day cycle (i.e. the time by which the average patient has three days to live), we can expect roughly thirty-five out of thirty-nine inpatients to take opioid medication(s) to manage pain.

Since the study will happen over about 180 days, this means the population size for the length of the study should be about 700 patients.

Therefore, assuming a 95% confidence interval, a 5% error margin, and a statistical significance level of .05, we have calculated a target sample size of 66 patients.

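### Primary objective 2 asks for a reduction in opioid dosage increases, but the planned data contain nothing against which a reduction could be measured

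*Combined protocol and SAP*

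**What the plan says.** Section 3.0 lists "Reduce opioid dosage increases" as the second primary objective and names no comparator or reference level.

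Section 4.0 describes a single open-label group: "Patients will choose to participate in a Marijuana adjuvant treatment group, receiving marijuana in combination with standard opioid therapy". The entry record is set out as "Patients' initial opioid dose, dosing schedule and numeric pain score will be recorded". Follow-up is then described as "For the duration of the study (at least five days) changes in opioid doses and numeric pain scores will be tracked daily". No run-in, look-back, historical cohort or untreated group is described anywhere.

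Under Analysis, section 4.0 plans the average number of increases and describes a favourable outcome as "lower average numeric pain scores, few dosage increases, lower opioid doses and subsequently less opioid therapy needed". Section 10.0 says that this average will be evaluated and adds no test, comparison, target or historical rate.

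Section 6.0 attaches one number to the count: three scheduled increases on the lower-strength regimen move a patient to the higher strength.

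**The concern.** Pain score and opioid amount each have a value at entry, so a change from entry can at least be calculated. The number of dosage increases has no such value, because it is counted only on study. The Analysis text reflects this: the other two measures are to be *lower*, while increases need only be *few*, and that word is never defined.

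A team following the plan exactly could read almost any mean count as success on a primary objective. The background section says the study will support widening the conditions for which marijuana may be prescribed in the state, so an unsupported claim of fewer increases could carry weight. A general remedy of analysing change from baseline would not reach this objective, because no baseline count exists.

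**Working it through.** **1. The sample size.** Section 5.0 gives a population of about 700, which reproduces as 180/9 × 35 = 700. The target of 66 fits a precision calculation for a single proportion with finite-population correction, if an unstated p of 0.05 (or 0.95) is assumed:

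- n0 = 1.96² × 0.05 × 0.95 / 0.05² = 72.99
- n = 72.99 / (1 + 71.99/700) = 66.2

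The calculation concerns a proportion, not a count of increases, so 66 gives objective 2 no specific support.

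**2. What each primary measure can be compared with.**

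| Measure | Value at entry | Untreated group | Stated threshold |
|---|---|---|---|
| Pain score | yes | none | none (*lower*) |
| Opioid amount | yes (initial dose and schedule) | none | none (*lower*) |
| Number of increases | no | none | none (*few*) |

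**3. What the trial would report.** The documents give no rate of increases, so I assume 0.1, 0.2 or 0.3 per patient-day. Exposure is 66 × 5 = 330 patient-days. Exact Poisson limits on the total, divided by 66, give:

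| Assumed rate per day | Expected total | Mean per patient | 95% CI |
|---|---|---|---|
| 0.1 | 33 | 0.5 | 0.34 to 0.70 |
| 0.2 | 66 | 1.0 | 0.77 to 1.27 |
| 0.3 | 99 | 1.5 | 1.22 to 1.83 |

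If the variance were twice the mean (an assumption), the middle row would become, by normal approximation, 1.0 ± 1.96 × √(2/66) = 1.0 ± 0.34, or 0.66 to 1.34.

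**4. What that result would mean.** Take the mean of 1.0 and three possible untreated means:

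- 2.0: 1.0/2.0 = 0.5, a halving
- 1.0: 1.0/1.0 = 1, no change
- 0.5: 1.0/0.5 = 2, a doubling

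The on-treatment rate is estimable. Without the untreated mean, neither the direction nor the size of an effect is.

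**5. Whether a reference can be found inside the plan.**

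- *Early against late study days.* Doses are tracked daily, so the rate can be compared over time. Both periods are on study drug.
- *The two capsule strengths.* Both groups receive study drug. Membership depends on recent marijuana use or on having already had three increases, so the outcome partly defines the group.
- *Records from before entry.* None are to be collected, and the approach is made early: "Patients will be notified of the study's existence through communication with the study's investigation team at time of admission". Some patients also enter already prescribed marijuana.

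**6. What an added chart comparison could offer.** The approximate 95% factor on a rate ratio, for K comparison charts of five days each and rate r, is exp(1.96 × √(1/(330r) + 1/(5Kr))). The protocol's figure of about 700 leaves 700 − 66 = 634 not enrolled. An alternative derivation takes "roughly thirty-five out of thirty-nine inpatients to take opioid medication(s) to manage pain" and the 12-day average stay: 35/12 × 180 = 525, leaving 459.

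| Usable charts K | Factor, r = 0.3 to r = 0.1 |
|---|---|
| 634 | 1.23 to 1.43 |
| 459 | 1.23 to 1.44 |
| 92 (20% of 459, assumed) | 1.29 to 1.56 |
| 459, variance twice the mean (assumed) | 1.35 to 1.68 |

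The first two rows assume that every chart is usable and that counts are Poisson, so they are best cases.

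**The case against.** The strongest reply is that the study is labelled exploratory or pilot and the planned analysis is already descriptive: averages, with no test. Section 4.0 also asks about a stabilising effect, and daily tracking lets the team see whether dosing settles. All of that stands. It limits the consequence, but it does not supply the reference that the word *reduce* requires.

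A reader might infer that, because the count starts at zero for everyone, nothing can fall within a patient and the objective is unanswerable in every sense. The documents do not support that. A cumulative count cannot fall, but a daily rate can, and the plan's data would show it. What they cannot show is that a fall is due to the study drug.

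A reader might also take the three-increase rule in section 6.0 as the missing benchmark. It is a treatment rule for one regimen and is not presented as a criterion of success.

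Nor should the contrast with objectives 1 and 3 be pushed too far. Their entry values permit a before-after difference, but without a control this does not separate drug effect from ordinary opioid titration. Objective 2 differs in lacking even that difference.

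**Conclusion.** The point holds as a fault in how the objective is stated. The planned data can estimate an on-treatment rate of increases, but cannot show a reduction. At an assumed mean of 1.0 per patient over five days, the same result (95% CI 0.77 to 1.27, Poisson) fits a halving, no change or a doubling, depending on an untreated mean that the trial will not observe.

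The structural conclusion does not depend on the assumed rates, on the Poisson model or on the size of any chart pool. It rests on the absence from the documents of an earlier count, a reference rate, a threshold and an untreated group. The change should be made. The exploratory label and the descriptive analysis keep it from being more serious than that.

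**What to change.** **Needed, at the cost of wording and a short analysis specification:**

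- Restate objective 2 in section 3.0 as estimating the on-treatment rate of opioid dosage increases per patient-day with a 95% CI. A patient-day denominator also suits follow-up of varying length in patients who need only a three-day life expectancy to enter (section 7.0).
- Specify in section 10.0 an interval that allows for overdispersion, for example from a negative binomial model with log patient-days as offset, or a patient-level bootstrap.
- Delete *reduce* from section 3.0 and *few* from the Analysis text in section 4.0. State that no conclusion of a reduction will be drawn from this measure. Any comparison of early with late days should be labelled descriptive.
- State, for this count, whether it covers scheduled increases only or also as-needed use. Section 5.0 admits both kinds of patient, and only section 6.0 says scheduled. Without this the rate is not defined.

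**Optional:** compare with opioid-treated inpatients who do not enrol, using the same counting rule and eligibility criteria, excluding patients already on marijuana, and aligning on days since admission and on cancer or non-cancer diagnosis. This needs ethics permission for chart data and abstraction time. Its precision depends on how many charts prove usable. It should be reported as exploratory, because patients choose whether to join and abstraction does not remove that.
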